#### 2.2.1.1 MINIMIZATION OF POTENTIAL RISKS

These risks are mitigated by utilizing qualified clinical Investigators who have training and are experienced in breast lift procedures and Renuvion procedures. In addition, risks are mitigated by including only those subjects that meet the study eligibility criteria. This study also includes evaluation of study subject satisfaction with the procedure.

#### 2.2.2 POTENTIAL BENEFITS

A possible benefit of using the Renuvion APR device in the breast areas is the potential for improvement in the appearance of lax tissue in the breast area utilizing a minimally invasive technique.

MEDICAL Appx Medical Corporation	
Protocol Number: APX-22-03	Effective Date: 23SEP2022 Revision No: 2.0
Title: Minimally Invasive Breast Lift Procedure Utilizing the Renuvion APR System	

## 3. STUDY PURPOSE

The purpose of this study is to evaluate the use of the Renuvion APR device as a minimally invasive lax breast procedure.

## 4. STUDY DESIGN AND ENDPOINTS

#### 4.1 DESCRIPTION OF THE STUDY DESIGN

This study is a prospective, single-center, non-randomized clinical trial. Up to 15 subjects will be enrolled and treated if they meet the inclusion/exclusion criteria and provide written informed consent. Investigator will assess baseline ptosis scale and volume assessment prior to treatment to confirm subject eligibility.

Subjects meeting all entrance criteria and confirmed eligible for study treatment will be enrolled. All Subjects will be treated using the Renuvion APR System by the study investigator. Standardized images will be taken prior to treatment and during each follow-up visits. Baseline assessments and pre-treatment images should be obtained within 30 days of the study treatment.

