#### 4.3 STUDY ENDPOINTS

#### 4.3.1 OUTCOME MEASURES

- 1. Independent Photographic Review of before and after images compared to baseline at D90 and baseline compared to D180.
- 2. Bilateral analysis of change to Morphometric breast measurements as per Brown, An Analysis of Ptosis at baseline and at day 30, 90, and 180 post-treatment.
- Bilateral analysis of change to Ptosis Classification per the Eyck et al, Rainbow Scale for Assessing Breast Ptosis at baseline and at day 180 post-treatment.
- 4. The Principal Investigator will complete a PGAIS assessing overall aesthetic improvement in the treatment area at day 30, 90, and 180 post-treatment.
- The subject will complete a SGAIS assessing overall aesthetic improvement in the treatment area at day 30, 90, and 180 post-treatment.
- 6. The subject will complete a Patient Satisfaction Questionnaire (PSQ) at the 180-day follow-up visit.
- 7. The subject will complete a Beast-Q survey at baseline and 180-day follow-up visit.

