#### 4.3.3.7 PTOSIS CLASSIFICATION

The Rainbow Scale for breast ptosis is validated for photographic review of the anterior-posterior view, the lateral view, and the oblique view, see **Figure 3**, **Figure 4**, and **Figure 5**, using the following grades at baseline at D180:

- Grade I (no breast ptosis): thoraco-mammary angle >90°, no visible breast ptosis.
- Grade II (mild breast ptosis): thoraco-mammary angle <90°, but nipple lies still above the level of the inframammary fold.
- Grade III (moderate breast ptosis): the nipple lies at the level of the inframammary fold, above the inferior breast contour.
- **Grade IV (severe breast ptosis)**: the nipples below the level of the inframammary fold but remains above the inferior breast contour.
- Grade V (extreme breast ptosis): the nipple lies below the level of the inframammary fold and at the inferior breast contour.

FIGURE 3: RAINBOW SCALE FOR ANTERIOR-POSTERIOR ASSESSMENT

FIGURE 4: RAINBOW SCALE FOR LATERAL ASSESSMENT

MEDICAL Apyx Medical Corporation	
Protocol Number: APX-22-03	Effective Date: 23SEP2022 Revision No: 2.0
Title: Minimally Invasive Breast Lift Procedure Litilizing the Renuvion APR System	

FIGURE 5: RAINBOW SCALE FOR OBLIQUE ASSESSMENT

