#### 5.2 INCLUSION CRITERIA

Subjects must meet all of the following criteria for study enrollment:

MEDICAL Apyx Medical Corporation	
Protocol Number: APX-22-03	Effective Date: 23SEP2022 Revision No: 2.0
Titles, Minimally, Investing Depart Life Department Life in the Department ADD Contern	

Title: Minimally Invasive Breast Lift Procedure Utilizing the Renuvion APR System

- Female subjects, ages 18 75 years old.
- ASA Physical Status Classification System Class I and Class II subjects.
- Breast Ptosis Class II and Class III as per the Eyck et al, Rainbow Scale for Assessing Breast Ptosis.
- Breast Cup Size A and Size B.
- Understands and accepts the obligation not to undergo any other procedures or treatments in the areas to be treated during study participation.
- Absence of physical conditions unacceptable to the investigator.
- Females of childbearing potential who are sexually active must be willing to use an approved method of birth control during study participation.
- Willing and able to comply with protocol requirements, including study-required images/photos, assessments/measurements, and returning for follow-up visits.
- Willing to release rights for the use of study photos, including in publication.
- Able to read, understand, sign, and date the informed consent.
- Able to communicate with the site via video and/or photographs, in the event of a virtual follow-up visit.

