#### 5.3 EXCLUSION CRITERIA

Subjects will be excluded if they meet any of the following criteria:

- Subjects presenting with ASA Physical Status Classification System Classes III or higher.
- Breast ptosis Class IV or more as per the Eyck et al, Rainbow Scale for Assessing Breast Ptosis.
- Breast Cup Size C, Size D or larger.
- Prior surgery or procedure in the breast area (i.e. implants, skin tightening procedures, breast reduction, etc.).
- Pregnant, lactating, or plans to become pregnant during study participation.
- Known hypersensitivity or allergy to tumescent anesthetic (lidocaine/ epinephrine).
- Known hypersensitivity or allergy to ibuprofen or other NSAIDS.
- Previous treatment in the study treatment area.
- Active systemic or local skin disease that may alter wound healing.
- Significant or uncontrolled medical condition that in the opinion of the investigator participation in the study may compromise the patient's health.
- History of autoimmune disease (excluding Hashimoto's thyroiditis).
- Known susceptibility to keloid formation or hypertrophic scarring.
- Cancerous or pre-cancerous lesions in the area to be treated.
- Possesses a surgically implanted electronic device (i.e., pacemaker).
- Serious mental health illness such as dementia or schizophrenia; psychiatric hospitalization in the past two years.
- Participation in any other investigational study within 30 days prior to consent and throughout study participation.
- Subject who, in the opinion of the investigator, is not an appropriate candidate for the study.

Protocol Number: APX-22-03	Effective Date: 23SEP2022 Revision No: 2.0
Title: Minimally Invasive Breast Lift Procedure Utilizing the Renuvion APR System	

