#### TABLE 6: STUDY REQUIRED PROCEDURES

	Baseline/ Pre-	Procedure	30 Days	90 Days	180 Days
	Screening 	(Day 0)	23-37 days	80-100 days	165-195 days
Informed Consent	Х				
Assess Inclusion/Exclusion Criteria	Х	As Needed			
Urine Pregnancy Test 	Х	Х			
Medical History	Х				
General Physical Exam	Х				
Ultrasound and Mammogram 	Х				
Review Medications	Х	Х	Х	Х	Х
2D Photographic Images 	Х	х	х	Х	Х
Ptosis Classification	Х				Х
Morphometric breast measurements	Х		Х	Х	Х
Breast-Q	Х				Х
Numeric Rating Scale (11-point NRS) 		X 	х	Х	Х
Study Procedure		Х			
Adverse Event Assessment		Х	х	Х	Х
Global Aesthetic Improvement Scale (GAIS) 			Х	Х	Х
Subject Satisfaction Survey					Х

 Pre-procedure Screening assessments to take place within 30 days prior to undergoing the procedure.

 Up to two urine pregnancy tests must be obtained prior to study procedure for females with child-bearing potential (one at pre-procedure screening and one on the day of the procedure prior to the procedure if screening and procedure are not performed on the same day).

2D-digital photographs will be taken and labeled according to Photography Instructions. Standard positioning and lighting will be used for all photographs.

 To be completed by the study subject on a day of the procedure (prior to the procedure and immediately following the procedure) and at all follow-up visits.

 NRS pain score will be captured prior to study treatment and immediately (within 60 minutes) after procedure.

To be completed by Investigator and study subject at day 90 and day 180 follow-up visits.

Prior to any breast procedure, ultrasound required for female patients below age 40; ultrasound and mammogram required for female patients aged 40 and above.

MEDICAL Apyx Medical Corporation	
Protocol Number: APX-22-03	Effective Date: 23SEP2022 Revision No: 2.0
Title: Minimally Invasive Breast Lift Procedure Utilizing the Renuvion APR System	

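### The one pre-treatment ptosis grade both admits subjects and serves as the Outcome 3 baseline, so the change carries regression to the mean of unknown size and direction

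*Combined protocol and SAP*

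**What the plan says.** Section 4.1 makes the baseline grade an eligibility test: "Investigator will assess baseline ptosis scale and volume assessment prior to treatment to confirm subject eligibility". Section 5.2 admits "Breast Ptosis Class II and Class III", and Section 5.3 excludes "Breast ptosis Class IV or more".

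Section 4.3.3.7 defines the lower two grades by the same angle: "Grade I (no breast ptosis): thoraco-mammary angle >90°, no visible breast ptosis" and "Grade II (mild breast ptosis): thoraco-mammary angle <90°, but nipple lies still above the level of the inframammary fold". Grades III and above are set by nipple level relative to the fold.

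Outcome 3 in Section 4.3.1 is the "Bilateral analysis of change to Ptosis Classification per the Eyck et al, Rainbow Scale for Assessing Breast Ptosis", taken at baseline and Day 180. Table 6 marks ptosis classification once in a combined baseline and pre-screening column and once at 180 days. The same table also schedules photographs on Day 0 and says "2D-digital photographs will be taken and labeled according to Photography Instructions". It does not say whether the Day 0 set is taken before the procedure.

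Sections 7.5.1 and 7.5.2 list screening and baseline separately, but neither adds a second ptosis grade. Section 7.4 confirms that there is no randomized comparison, and Section 10.1 plans descriptive statistics only.

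**The concern.** When subjects are chosen because a noisy reading fell in a window, and that same reading is then the starting point for change, the next reading tends to move back towards the candidate's true value even if nothing has happened. Here the window has two edges. A woman read as Grade I never enters, so no I-to-II move can offset a noise-driven II-to-I move. A woman read as Grade IV never enters either, so no IV-to-III move can offset a noise-driven III-to-IV move. For a Grade II entrant, the 90° line that admits her is also the only line she can cross to improve.

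With one arm and descriptive statistics, the tally of grade changes is the whole result for Outcome 3. Nothing planned shows how often a grade changes without treatment, so a reader could not tell a one-grade lift from re-reading error. Masking the Day 180 grader would not cure this, because the distortion comes from selection on the first reading.

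**Working it through.** The plan gives no figure for Outcome 3 to reproduce: no reading error, expected change or success rule, and no calculation behind the 15 subjects. Step 1 rests on the text. Steps 2 to 5 assume no treatment effect, independent reading errors and invented candidate distributions, as stated.

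**Step 1, the structure.** Entry is Grade II or III (Sections 5.2 and 5.3). The only grade better than II is I, across 90° (Section 4.3.3.7). One pre-treatment grade is scheduled (Table 6) and it confirms eligibility (Section 4.1). The selecting reading and the baseline reading are therefore the same.

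**Step 2, the 90° line alone.** Let the true angle T be normal with mean m and SD 12°, the screening reading S = T + e1 and the Day 180 reading D = T + e2, each error with SD s. The correlation between readings is 144/(144 + s²), for example 144/208 = 0.69 at s = 8°. The quantity is P(D > 90 given S < 90).

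| Reading SD | m = 75° | m = 80° | m = 85° |
|---|---|---|---|
| 5° | 5.0% | 8.3% | 12.5% |
| 8° | 8.5% | 13.2% | 18.9% |

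Over s = 3° to 10° the range is 2.9% to 22.6%. With candidate SD 10° and means from 70° to 90°, it is 0.6% (mean 70°, s = 2°) to 29.2% (mean 90°, s = 8°). If all 15 were Grade II, s = 8° gives 15 × 0.085 = 1.3 to 15 × 0.189 = 2.8 false improvers. These are gross counts across one line and say nothing about the net.

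**Step 3, all boundaries.** Add nipple height above the fold, with SD 1.2 cm between candidates. Grade III is taken as within ±0.5 cm of the fold (the documents give no tolerance) and Grade IV as lower. Select on a screening read of II or III and compare it with an independent Day 180 read, using 2,000,000 simulated candidates per setting. Net drift is percent improved minus percent worsened.

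| Mean angle | Mean height | Reading SD | Net drift, points |
|---|---|---|---|
| 80° | 1.5 cm | 5°, 0.3 cm | 11.4 - 5.9 = +5.5 |
| 75° | 0.5 cm | 5°, 0.3 cm | -1.8 |
| 80° | 0 cm | 5°, 0.3 cm | -3.6 |
| 80° | -0.5 cm | 5°, 0.3 cm | -7.7 |
| 85° | 3.0 cm | 8°, 0.5 cm | about +18 |

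In the second row 60% of entrants are Grade II, and the drift is still negative.

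**Step 4, a separate baseline.** Given the true state, a Day 0 read and a Day 180 read made in the same way have the same distribution, and neither was used for selection. So P(better) = P(worse) and net drift is zero. In the central setting (first row) the simulation gives 9.3% improved and 9.3% worsened.

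P(2 or more of 15 improve) = 1 - (1-p)^15 - 15p(1-p)^14, counting one grade per subject:
- p = 0.114 gives 0.52
- p = 0.093 gives 0.41

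The expected number of false improvers falls from 15 × 0.114 = 1.7 to 15 × 0.093 = 1.4. So 9.3/11.4, about 82%, of the false improvers are ordinary noise. With mean height 0 cm the separate baseline raises false improvement, from 11.8% to 14.2%, because there the selection had been suppressing it.

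**Step 5, a different model.** Use a latent severity scale with grade cut-points one unit apart, between-subject SD 1 grade and reading SD 0.3 grade. Improved/worsened among all entrants is 22.3%/10.6% with candidates centred on the I/II line, 15.9%/15.9% on the II/III line and 13.2%/18.9% at mid-Grade III. In the first of these, a separate baseline gives 16.8%/16.6%. The pattern is the same.

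**The case against.** The strongest objection concerns direction. A reader might infer that the plan is tilted towards showing improvement, since Grade I is shut out and 90° is both the entry and the improvement line. The documents do not support that. The Grade IV exclusion creates the mirror-image effect at the other edge, noise also moves Grade II to III, and nothing in the protocol says where candidates will lie. Steps 3 and 5 give negative drift when candidates sit near or below the II/III line. This part of the objection stands.

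A reader might also infer that a new baseline removes the false improvers. It does not: Step 4 shows that it removes the net drift and leaves most of the noise. That stands too.

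Other points stand in part. Outcome 3 is one of seven unranked measures, no improver is defined for it, and a table showing worsening is already compatible with the wording. The eight morphometric measurements in Section 4.3.3.8 also track breast position on continuous scales. Section 4.3.3.1 has sponsor staff review baseline photographs for subject selection, which may catch gross misgrading. But that review records no second grade, and the blinded reviewers in Section 4.3.3.1.1 only choose the post-treatment image. None of these gives a baseline free of the selection or a rate of change without treatment.

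**Conclusion.** The concern holds as a structural flaw in Outcome 3: change is measured from the reading used to select, in a single arm, with no estimate of reading error. For Grade II entrants, entry and improvement turn on the same 90° line. The protocol never says outright that the screening grade is the Outcome 3 baseline, but Section 4.1 and the single pre-treatment entry in Table 6 leave no other reading.

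The size and direction of the drift cannot be derived from the documents. In the settings tried it ran from about -8 to about +18 points, with +5.5 in the central one. Every figure rests on assumed candidate distributions and reading errors, so the range is illustrative and not a bound. It would be wrong to report that the plan is biased towards improvement in general. Correcting this is a cheap improvement; the study does not depend on it.

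**What to change.** In Section 4.3.3.7 and Table 6:

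- Keep the screening grade for eligibility only.
- State that the Day 0 photographs are taken before the procedure.
- After Day 180, have the same delegated grader grade each breast from the Day 0 photographs without sight of the screening grade. Use that grade as the baseline for Outcome 3.
- If screening and procedure fall on the same day, re-read the pre-procedure photographs and state that this captures reader error only. Error from pose or image is then shared by both reads and is not removed.
- Report breasts improved, unchanged and worsened. Beside them give the share whose screening grade and second pre-treatment grade differ, as the rate of grade change without treatment.
- State that the retrospective grade does not reopen eligibility.

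The cost is a few sentences and at least 15 × 2 = 30 extra breast gradings, more if the three views are graded separately. It needs no new visit, subject or procedure. In the Step 3 settings, roughly 9% to 19% of entrants would have an outcome baseline of Grade I or IV, so the results table needs rows for those grades. The change may raise or lower the count of improvers; its purpose is to remove the net drift and to show the noise.

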#### 4.2 DURATION OF STUDY

Recruitment for this study may take approximately four months. Following the treatment visit, subjects will be followed for a total duration of 180-days, after which, data will be analyzed. Therefore, the anticipated total duration of the study is approximately twelve months.

#### 4.3 STUDY ENDPOINTS

#### 4.3.1 OUTCOME MEASURES

- 1. Independent Photographic Review of before and after images compared to baseline at D90 and baseline compared to D180.
- 2. Bilateral analysis of change to Morphometric breast measurements as per Brown, An Analysis of Ptosis at baseline and at day 30, 90, and 180 post-treatment.
- Bilateral analysis of change to Ptosis Classification per the Eyck et al, Rainbow Scale for Assessing Breast Ptosis at baseline and at day 180 post-treatment.
- 4. The Principal Investigator will complete a PGAIS assessing overall aesthetic improvement in the treatment area at day 30, 90, and 180 post-treatment.
- The subject will complete a SGAIS assessing overall aesthetic improvement in the treatment area at day 30, 90, and 180 post-treatment.
- 6. The subject will complete a Patient Satisfaction Questionnaire (PSQ) at the 180-day follow-up visit.
- 7. The subject will complete a Beast-Q survey at baseline and 180-day follow-up visit.

#### 4.3.2 SAFETY ENDPOINTS

- 1. Analysis of adverse events through the D180 post-treatment visit.
- During study treatment, the subject's pain levels will be monitored using the 11-point Numeric Rating Scale (NRS). The average pain score for the entire region treated will be recorded. Pain scores will be recorded at all follow-up visits.

MEDICAL Appx Medical Corporation	
Protocol Number: APX-22-03	Effective Date: 23SEP2022 Revision No: 2.0
Title: Minimally Invasive Breast Lift Procedure Litilizing the Renuvion APR System	

#### 4.3.3 EVALUATION TOOLS

The following evaluation tools will be used in this study:

#### 4.3.3.1 2-DIMENSIONAL PHOTOGRAPHY

Two-dimensional (2D) photographic images will be captured utilizing the site's current photography system. The same standardized photography views will be used throughout the study. Images will be monitored for quality to ensure standardized images and subject alignment between baseline and follow-up visits. Study staff should review photos with particular care during each visit to ensure consistent alignment.

Baseline images may be taken within 30 days prior to study treatment. Subject baseline photos are reviewed by Apyx staff prior to study treatment to ensure proper subject selection and adequate image capture.

#### 4.3.3.1.1 INDEPENDENT PHOTOGRAPHIC ASSESSMENTS

Three experienced, blinded photographic reviewers will perform a qualitative analysis/review of the pretreatment and post-treatment sets of images of each subject in a blinded and randomized order. Each blinded reviewer will choose which image is the post-treatment image. Success will be correct posttreatment image selection by at least 2 out of 3 reviewers. The percentage of subjects with a correct posttreatment image selection will be calculated.

Assessment of each subject's baseline and follow-up images viewed simultaneously will be performed by the Independent Photographic Reviewers (IPR) who will be blinded to the study subject's visit (baseline and follow-up visit). Each IPR will view each subject's randomized pre-treatment and post-treatment images and assess which set of images represent the subject's post-treatment images. Each photograph will have a unique identification number, but the sets of images will not be arranged in any specific order (i.e., randomized order).

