#### 4.3.3.1.2 INDEPENDENT PHOTOGRAPHIC REVIEW EVALUATION PROCESS

Each blinded assessor will be provided with identical photos to be assessed. The pre-treatment and posttreatment photos will be consistent in lighting, subject positioning, and focus. Each photo's visit interval, i.e., pre-treatment and post-treatment, will NOT be marked. The images placement (right or left) will be randomly ordered for pre-treatment and post-treatment images. Images for each subject will be grouped together into one set with all pre-treatment and post-treatment images in the same location (right/left) for the subject set.

Each blinded assessor will conduct their assessment independently with no input from another blinded assessor.

Each blinded assessor compares the Left and Right photo for change that may be striking (substantial and immediately noticeable), readily apparent but modest in nature, or slight and subtle in nature that may require close examination. Assessors should look through each view and assess change. Enough time should be allowed to do this for each subject, so the assessments are not rushed.

The assessor chooses which photo they believe to be the post-treatment photo (i.e., Left photo or Right photo) once all images in the subject set have been reviewed.

Post-Analysis Coding of Masked Assessment:

- If the assessor incorrectly chooses the post-treatment photo, this will be coded as an "Incorrect post-treatment selection".
- If the assessor correctly chooses the post-treatment photo, this will be coded as a "Correct post-treatment selection".

Λργχ *	
MEDICAL Apyx Medical Corporation	
Protocol Number: APX-22-03	Effective Date: 23SEP2022
	Revision No: 2.0
Title: Minimally Invasive Breast Lift Procedure Utilizing the Renuvion APR System	

• Success will be determined by correct identification of post-treatment photographs by at least two out of three blinded, independent reviewers.

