#### 10.2 SAMPLE SIZE

The study will include up to 15 treated subjects from a single EU site.

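### The masked photo review records three choices per subject but plans to report only the 2-of-3 success percentage, with no reference to the 50% expected from guessing

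*Combined protocol and SAP*

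**What the plan says.** Section 4.3.1 lists the photo review as the first outcome, at two time points: "Independent Photographic Review of before and after images compared to baseline at D90 and baseline compared to D180". Section 4.3.3.1.1 describes the reading: "Three experienced, blinded photographic reviewers will perform a qualitative analysis/review", and "Each blinded reviewer will choose which image is the post-treatment image". The subject-level rule is "Success will be correct posttreatment image selection by at least 2 out of 3 reviewers", and the only summary named is "The percentage of subjects with a correct posttreatment image selection will be calculated".

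Section 4.3.3.1.2 has each individual choice classified as right or wrong ("If the assessor correctly chooses the post-treatment photo, this will be coded as a" correct selection, with a matching code for an incorrect one), so the finer data will exist. It also states "Each blinded assessor will conduct their assessment independently with no input from another blinded assessor", randomises left/right placement, and keeps all images from one visit on the same side within a subject's set.

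Section 10.1 limits the analysis to descriptive statistics. Section 10.2 gives the size without a derivation: "The study will include up to 15 treated subjects from a single EU site". Neither section mentions a distribution of the number correct, a rate per reviewer, an interval or a chance benchmark.

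**The concern.** The success rule treats a subject identified by all three reviewers like one identified by two, and a subject missed by all three like one missed by two. With at most 15 subjects, that makes the reported figure coarse.

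The choice is two-way, so a reviewer who sees nothing is still right half the time, and the 2-of-3 rule also succeeds half the time. A success percentage printed without that reference invites the reader to compare it with zero.

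This matters here because there is no control arm and the other efficacy outcomes are not protected by masking. The GAIS is scored by the investigator (or a delegated clinician) and by the subject, both referring to the pre-treatment photographs. The satisfaction questionnaire and Breast-Q are subject-reported. No masking is described for the ptosis grade or the morphometric measurements. The precision and clarity of the photo review therefore bound what the study can say objectively.

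**Working it through.** The plan states no power, precision or benchmark for this outcome, so there is no figure of its own to reproduce.

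**Inputs from the documents.** Up to 15 subjects (10.2); 3 reviewers, one two-way choice each, success at 2 or more correct (4.3.3.1.1); left/right placement randomised per subject set (4.3.3.1.2). This gives 15 × 3 = 45 choices per time point if all subjects are evaluable.

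**Assumptions, not in the documents.** Per-reviewer accuracy p, between-reviewer correlation rho within a subject, a one-sided 2.5% level, and all 15 subjects evaluable.

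**1. Chance level of the rule.** P(at least 2 of 3) = p³ + 3p²(1 − p). At p = 0.5 this is 0.125 + 0.375 = 0.50.

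**2. What the percentage can show against 50%.** The exact binomial tail at 0.5 with n = 15 is 0.059 for 11 or more and 0.0176 for 12 or more. So 12/15 (80%) is the smallest count below 0.025. Its exact 95% interval is 0.52 to 0.96.

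**3. What 12/15 can conceal.**
- Fewest correct choices: 12 × 2 + 3 × 0 = 24, or 24/45 = 53%.
- Most correct choices: 12 × 3 + 3 × 1 = 39, or 39/45 = 87%.

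An exact subject-level sign-flip comparison (score 2k − 3 for k correct, sign reversed with probability one half) gives one-sided p = 0.38 for the first pattern and 0.0006 for the second.

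**4. One strong reviewer.** If one reviewer is always right and the other two guess, a subject fails only when both guessers are wrong: success probability 1 − 0.5² = 0.75. The chance of 12 or more of 15 is then 0.46. The success percentage alone would not reveal this; counts per reviewer would.

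**5. Size of the gain from the 0 to 3 score.** The number correct per subject is modelled as beta-binomial with mean p and correlation rho. The 2-of-3 result is tested by exact binomial (12 or more of 15), the score by the exact sign-flip. Example at p = 0.7, rho = 0: subject success is 0.343 + 0.441 = 0.784, and P(12 or more of 15) = 0.588.

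| p | rho | 2-of-3 rule | 0–3 score |
|---|---|---|---|
| 0.6 | 0 | 0.169 | 0.182 |
| 0.6 | 0.4 | 0.107 | 0.128 |
| 0.7 | 0 | 0.588 | 0.671 |
| 0.7 | 0.3 | 0.397 | 0.486 |
| 0.7 | 0.8 | 0.302 | 0.333 |
| 0.7 | 1 | 0.297 | 0.297 |
| 0.8 | 0 | 0.937 | 0.976 |
| 0.8 | 0.3 | 0.778 | 0.873 |
| 0.8 | 1 | 0.648 | 0.648 |

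Entries are the chance of excluding guessing. The squared signal-to-noise ratio, score over rule, is 1.20 to 1.33 for p = 0.6 to 0.7 and rho = 0 to 0.4. It is 1.00 at rho = 1 for any p, and 0.65 at p = 0.9 with rho = 0.

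**6. Why the choices cannot simply be pooled.** The effective number of choices is 45/(1 + 2·rho): 45 at rho = 0, 25 at rho = 0.4, 15 at rho = 1. Treating the 45 as independent gives an apparent power of 0.746 at p = 0.7, against 0.671 or less for the subject-level test.

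**The case against.** The strongest objection is that the study is descriptive. It sets no hypothesis, alpha or benchmark, so power against guessing measures the plan against a goal it never adopted. That stands: the figures in the table are illustrations, and any test should be supportive only.

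The gain also depends on unknowns. All reviewers see identical photographs and share a training session in which scoring is discussed, so agreement may be high. At rho = 0.8 and 70% correct the difference is 3 points. At 60% correct the tabulated differences are 1 to 2 points, and power is at or below 0.18 either way. That stands too.

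The 2-of-3 rule gives some protection against a dominant reader, since a second reviewer must agree before a subject counts as a success. This limits, but does not remove, the effect in step 4.

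Three stronger readings are tempting, and the documents do not support them:
- A reader might infer that the reviewers' choices are thrown away. They are coded individually, and Section 10.1 does not bar tabulating them. It merely does not commit to it.
- A reader might infer that the 0 to 3 score is better almost everywhere. It gains nothing when reviewers always agree, and on the signal-to-noise measure it is worse at 90% correct with independent reviewers.
- A reader might infer that the 2-of-3 analysis is wrong. It is a valid subject-level summary; it is only incomplete.

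**Conclusion.** The point holds as a reporting weakness in the only outcome with masked raters. The planned percentage cannot distinguish 53% from 87% correct choices at a reported 12/15, and it carries no reference to the 50% expected from guessing. Those two statements follow from the design alone, with 15 evaluable subjects.

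The gain in sensitivity from using all three choices is secondary and modest: about 8 to 9 points at 70% correct with rho from 0 to 0.4, 3 points at rho = 0.8, and none at rho = 1. It rests on assumed accuracy, correlation and alpha. No figure stated in the protocol is wrong. The change is still worth making before the images are read, because a summary fixed in advance carries more weight than one chosen after the results are known.

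**What to change.** Keep the 2-of-3 success percentage. Add to Sections 4.3.3.1.1 and 10.1:

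> For D90 and for D180 separately, the number of correct choices per subject (0, 1, 2, 3) is tabulated. The mean proportion correct is reported with a 95% interval using the subject as the unit and is read against 50% (guessing), with a supportive exact subject-level sign-flip comparison. The number correct is also shown for each reviewer. The 45 choices are not treated as independent.

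The sign-flip is valid whatever the agreement between reviewers, provided each subject's set is placed left or right at random with equal probability. If the sponsor wants no test at all, the distribution, the subject-level interval and the counts per reviewer still repair the main weakness.

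The cost is a short paragraph and one table for each time point. No additional reads, reviewers, images or subjects are needed.
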